Evaluating a prototype medical device like AIDAVA requires to work with patients who agree to collaborate and share their personal data. In the case of patients recruited through hospitals, this is only acceptable with approval from the local Ethical Committees in each hospital on the basis of a structured research study protocol, with clear description of objectives, and approach including a close monitoring of each patient with study nurses during the evaluation. It goes without saying that the prototype provided to the users needs to be tested following good software development practices including unit test, integration test and mainly user acceptance test; this testing approach is part of the *Deliverable D 3.6 - G1 installed for testing.* System reliability, safety and security are part of the business requirements and included in the testing approach in D3.6.

Task 1.4 "Details testing scenario to assess performance/acceptance of prototypes", in scope of this document, is responsible for describing the different steps and activities needed to formally evaluate the prototype with on-site patients using their personal data in real life settings. The assessment study includes Generation 1 and Generation 2 of the AIDAVA prototype. As it was decided to keep as much of the same patient as possible across the 2 generations of the prototype, the assessment study also must cover the period of inactivities for the patients during the two generations.

The first objective of the task was to define an end-to-end testing scenario from data sources, ingestion into the AIDAVA environement, curation and then to publishing based on the use cases defined in Deliverable D1.1 and in compliance with ELSI requirements. An important point in the study was to identify practical and measurement endpoints to measure effectiveness of the prototype and user acceptability. The scenario was developed and agreed upon with key user representatives, hospital staff and Health Data Intermediaries (HDI) representatives; it was also validated by the patient consultants to ensure its feasibility.

³ A prototype does not need to go through MDR certification ; at the end of the project the idea is to develop a product medical device that will require MDR.

The second objective was to translate this testing scenario into a set of formal documents to be submitted to the different local ethical committees for approval.

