4.1 Overall Design

The assessment study will be a cohort, 3 arms, prospective¹³ study involving 30 patients (15 breast cancer and 15 CVD) + 3 expert curators in each site. It will be based essentially on available data, collected during clinical care (see Section 10.1 for detailed description of data sources), but will also include some prospective data from medical devices and Quality of Life questionnaire

There will be 3 arms that will allow comparison across these different populations of users.

- "G1 and G2" patients who contributed to evaluation of G1 and G2.
- "Single Generation" patients who contribute to the evaluation of only one generation of the prototype (G1 or G2)
- Expert data curators

There will be 4 epochs

- Epoch 1 will last 1 week and take place just before deployment and evaluation of G1; it will allow to gather information from the expert curator on the current situation/curation process and to provide a dedicated training to the curators.
- Epoch 2 will last for 2 weeks, and is expected to take place in the period of July September 2024. Patients will be requested to ingest their data with the support of the prototype, and to curate them. Whenever needed, the data expert curator will be able to support them.
- Epoch 3 will last for 16 to 18 months: "wash out" period during which G2 of the prototype will be developed;
- Epoch 4 will last for 2 weeks and is expected to take place in the period February/March 26. Patients and curators will be requested to assess Generation 2 (G2) of the prototype, by performing the same task as in Epoch 2 to enable comparison of the performance of the 2 generations of the prototype.

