5.2 Study Population

The study participants include

- Patients who met the inclusion/exclusion criteria specified below
- **Expert data curators,** i.e. staff from the hospital, responsible for the maintenance of the local AIDAVA registry, extracting data from the patient medical record and inserting them into the registry
- **Breast Cancer specialists**: staff from the hospital responsible for treating patients and active in clinical research with the local breast cancer registry.
- **CVD practitioners:** staff from the hospital responsible for treating CVD patients

The staff from the hospital that will collaborate on the study is specified in Section 10.4.

Inclusion criteria (MUST)	 Data available in EHR within related medical centre Owner and user of a smartphone Consent to give access to their personal data (based on scope provided in the Informed Consent Form) to the data curator identified in the hospital Agree to sign a collaboration agreement with the relevant HDI - for the duration of the study Agree to test the AIDAVA prototype (G1 and G2) and to delegate to a representative data curator in case of issues
Inclusion criteria for BC patients (MUST)	 Gender: All History of a confirmed diagnosis of breast cancer treated with surgery and radiotherapy
Inclusion criteria for CVD patients	Gender: AllConfirmed diagnosis of symptomatic type 1 acute Myocardial Infarction
Inclusion criteria (NICE TO HAVE)	Health and digital literacy
Exclusion criteria	 Data not accessible (for instance for technical reason) Vulnerable persons Children/minors Inability/unwillingness to use smartphone applications Does not use a smartphone Russian only as a language (in Estonia)

The patients will be selected based on the following inclusion/exclusion criteria.

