7.2 Lost to Follow up

A participant will be considered lost to follow-up if the participant repeatedly fails to return for scheduled visits and is unable to be contacted by the study site.

The following actions must be taken if a participant fails to return to the clinic for a required study visit:

- The site must attempt to contact the participant and reschedule the missed visit as soon as possible, counsel the participant on the importance of maintaining the assigned visit schedule, and ascertain whether the participant wishes to and/or should continue in the study.
- Before a participant is deemed lost to follow-up, the investigator or designee must make every
 effort to regain contact with the participant (where possible, telephone calls, and if necessary, a
 certified letter to the participant's last known mailing address or local equivalent methods).
 These contact attempts should be documented in the participant's medical record.
- Should the participant continue to be unreachable, the participant will be considered to have withdrawn from the study.

In the AIDAVA assessment study, there is a risk of patient discontinuation because of the 16 to 18 months time lag between EPOCH 1 and EPOCH 3. To decrease the risk and keep the momentum / interest of patients we will issue regular newsletters (one page every 3 to 4 months). In case of an important discontinuation we might need to ask sites to recruit new patients for EPOCH 3.

In case of withdrawal, patients will be requested what they wish to do with the PHKG containing their data and available in the system; they will be able to receive these data or to request deletion of the PHKG in the same way that at the end of the study (see Section 4.4). In case of lost to follow-up, the PHKG of the related patient will be deleted at the end of the study.

8. Study Assessments and Procedures

- Study procedures and their timing are summarised in the SoA. Protocol waivers or exemptions are not allowed.
- Adherence to the study design requirements, including those specified in the SoA, is essential and required for study conduct.
- All screening evaluations must be completed and reviewed to confirm that potential participants meet all eligibility criteria. The investigator will maintain a screening log to record details of all participants screened and to confirm eligibility or record reasons for screening failure, as applicable.

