9.3 Statistical Analyses

Three tests have be retained

- **Paired t-test**: statistical test that compares the means of two related groups, where each subject is measured at two different time points or under two different conditions. It is used to determine if there is a significant difference between the two groups.
- Mann-Whitney U test (unpaired t-test): non-parametric statistical test used to compare the medians of two independent groups. It is often used when the data are not normally distributed or when the sample sizes are small.
- Wilcoxon signed-rank test: non-parametric statistical hypothesis test used to compare two populations with two matched samples.

Primary Endpoint(s) Analysis

The endpoints are defined in Section 9.2 will be used to support the analysis

Computed	Description of measures	Test & meaning (per H1)			
	Population: Expert Curators				
E1	Difference between data points 1 and 2: E1.M2.1△ = M2.1@PDP1 - M2.1@PDP2 E1.M2.2△ = M2.2@PDP1 - M2.2@PDP2	Paired t-test H1: less time spent in curation in G1 than in G0 for expert curators			
E2	Difference between data points 2 and 3: E2.M1-Δ = M1@PDP2 - M1@PDP3	Paired t-test H1: G2 is more usable than G1 for expert curators			
	E2.M2.1∆ = M2.1@PDP2 - M2.1@PDP3 E2.M2.2∆ = M2.2@PDP2 - M2.2@PDP3	H1: less time spent in curation in G2 than in G1 for expert curators			
	Population:	Patients			
P1	Difference in data points 4 and 5 (i.e. difference between G1 and G2 for arm where patients used G1 AND G2)	Paired t-test (effect of system + training/experience from G1)			
	P1.M1- = M1@PDP4 - M1@PDP5	H1: G2 more usable than G1			
	P1.M2.x∆ = M2.x@PDP4 - M2.x@PDP5	H1: G2 requires less time for curation than G1 H1: G2 enables curation with less human intervention than G1			
	P1.M3-∆ = M3@PDP4 - M3@PDP5	H1: G2 provide same or higher quality than G1			
P2	Difference in data points 6 and 7 (i.e. difference between G1 and G2 for arm where patients used G1 OR G2)	Unpaired t-test (effect of system only)			
	P2.M1- = M1@PDP6 - M1@PDP7	H1: G2 more usable than G1			
	P2.M2.x∆ = M2.x@PDP6 - M2.x@PDP7	H1: G2 requires less time for curation than G1 H1: G2 enable curation with less human intervention than G1			
	Ρ2.Μ3-Δ = M3@PDP6 - M3@PDP7	H1: G2 provide same or higher quality than G1			

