A1	Sum across patient arms for G1 A1.M1 = M1@PDP4 + M1@PDP6 A1.M2.x = M2.x@PDP4 + M2.x@PDP6 A1.M3.x = M3.x@PDP4 + M3.x@PDP6 A1.M4.x = M4.x@PDP4 + M4.x@PDP6	Descriptive Statistics Performance in G1 of the AIDAVA system.			
A2	Sum across patient arms for G2	Descriptive Statistics			

Computed	Description of measures	Test & meaning (per H1)
	A2.M1 = M1@PDP5 + M1@PDP7 A2.M2.x = M2.x@PDP5 + M2.x@PDP7 A2.M3.x = M3.x@PDP5 + M3.x@PDP7 A2.M4.x = M4.1@PDP5 + M4.x@PDP7	Performance in G2 of the AIDAVA system.
A3	Difference in A1 and A2 (i.e. difference between G1 and G2 across all patients)	Unpaired t-test
	Α3.Μ1-Δ = Α1.Μ1 - Α2.Μ1	H1: G2 more usable than G1
	A3.M2.xΔ = A1.M2.x - A2.M2.x A3.M3.x-Δ = A1.M3.x - A2.M3.x	H1: G2 requires less time for curation than G1 H1: G2 enable curation with less human intervention than G1
	A3.M4.X-∆ = A1.M4.x - A2.M4.x	Wilcoxon signed-rank test H1: The NLP system developed in G2 yields a higher precision than the NLP system from G1. H1: The NLP system developed in G2 yields a higher recall than the NLP system from G1.
A4	Difference in P1 and P2 (difference between the 2 patient arms)	Unpaired t-test (effect on training/experience) There is a difference in performance due to training/experience with the system : patients having used G1 are more/not more effective in G2 than patients who work with only one generation of the prototype (G1 or G2)
	Α4.Μ1-Δ = P1.Μ1-Δ - P2.Μ1-Δ	H1: G2 more usable than G1 (due to experience during G1)
	A4.M2.x-Δ = P1.M2.x-Δ - P2.M2.x-Δ A4.M3.x-Δ = P1.M3.x-Δ - P2.M3.x-Δ	H1: G2 requires less time for curation than G1 as patients are more experienced H1: There are less questions of the system unanswered during G2 than in G1 as the patient acquired experience in G1
	A4.M4	Not useful

Secondary Endpoint(s) Analysis

Description of measures	Test & meaning (per H1)
Breast Canc	er
Difference in data points 0 and 1 (i.e. difference between G0 and G1 across a sample of 15 patients) U0.TBCx- Δ = TBCx@SDP0 - TBCx@SDPA U0.EBCx- Δ = EBCx@SDP0 - EBCx@SDP1 U0.ACCx- Δ = ACCx@SDP0 - ACCx@SDP1	Unpaired t-test H1: G2 has more (or same) accuracy than G1 while keeping the same time saving and duration
	Descriptive Statistics around performance in G1 of the AIDAVA system (e.g. mean,)

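### P2 compares G1 patients who did not return with new G2 recruits, so P2 and A4 cannot carry their causal labels, and A4's named test cannot be run

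*Protocol*

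**What the plan says.** Section 4.1 defines a single-generation arm as "patients who contribute to the evaluation of only one generation of the prototype (G1 or G2" and gives no rule for who enters it. Section 5.2 makes it an inclusion criterion for all patients that they "Agree to test the AIDAVA prototype (G1 and G2) and to delegate to a representative data curator in case of issues". The Introduction of the main deliverable states the retention aim: "As it was decided to keep as much of the same patient as possible across the 2 generations of the prototype".

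Section 7.2 accepts that "there is a risk of patient discontinuation because of the 16 to 18 months time lag between EPOCH 1 and EPOCH 3", and adds: "In case of an important discontinuation we might need to ask sites to recruit new patients for EPOCH 3". (Section 7.2 numbers the periods differently from Section 4.1, where G1 and G2 are tested in Epochs 2 and 4.) Section 4.4.2 gives first-time G2 patients their own screening window, September 2025 to February 2026.

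In Section 9.3:

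- P1 is the paired G1-to-G2 change in patients who used both (PDP4, PDP5), read as system plus experience.
- P2 is the "Difference in data points 6 and 7", tested unpaired and read as "effect of system only".
- A4 is P1 minus P2, tested with an unpaired t-test and read as: "There is a difference in performance due to training/experience with the system".

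The alternative hypothesis in Section 9.1 attributes most of the improvement to the tool and some of it to training.

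**The concern.** P2 can be read as a pure system effect only if G1-only and G2-only patients would score alike on the same tool. The protocol's own rules make that doubtful. PDP6 holds people who agreed to both generations and stopped, while PDP7 holds people who have just joined. If those who found G1 difficult are more likely to leave, G2 looks better than G1 even when the tool has not changed, and A4 then understates or reverses a real gain from experience.

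The split matters because Section 9.1 hypothesises about it. P1 mixes the two effects, A3 pools returning and new patients, and E1 and E2 concern curators. Only P2 and A4 are meant to separate tool from experience in patients.

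**Working it through.** **Inputs from the protocol.** Planned patients: 15 × 2 use cases × 3 sites = 90, which reproduces Section 9.4. The same section regards 50 to 80 subjects as sufficient. If that is read as the number retained, 10 to 40 of 90 (11% to 44%) would be G1-only. The protocol gives no alpha, SD, drop-out rate or link between drop-out and outcome, so those are assumed below (two-sided 0.05 throughout).

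**Decomposition.** Write contrasts as G2 minus G1 with higher meaning better (the protocol writes G1 minus G2). Let S be the system effect, X the experience effect, and D the mean of new recruits minus the mean of non-returners on the same tool. Then

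- P1 = S + X (in returners)
- P2 = S + D
- A4 = P1 − P2 = X − D

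P2 equals S and A4 equals X only if D = 0 and S is the same in both patient arms.

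**How D arises.** Let a share w of G1 patients return, and let non-returners score d lower at G1 than returners. The overall G1 mean is m = w·M4 + (1 − w)·M6, so M6 = m − w·d. If recruits resemble the original entrants, M7 = m + S. Hence P2 = M7 − M6 = S + w·d, and D = w·d.

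**SUS illustration (all assumed).** w = 2/3, so 90 × 1/3 = 30 non-returners, with 30 recruits, SD 15 and S = 0. Rejection rates from the noncentral t:

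| d (SUS points) | Shift in P2 = w·d | P2 significant, 30 per group | 15 per group |
|---|---|---|---|
| 5 | 3.3 | 14% | 9% |
| 10 | 6.7 | 39% | 22% |
| 15 | 10.0 | 72% | 42% |

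**In SD units**, applicable to any measure including time, with S = 0 (normal approximation):

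| n per group | D = 0.2 SD | D = 0.5 SD | D = 0.8 SD |
|---|---|---|---|
| 10 | 7% | 20% | 43% |
| 25 | 11% | 42% | 81% |
| 40 | 15% | 61% | 95% |

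**Simulation** of 90 patients with S = 0 and X = 0.3 SD, where the tendency to drop out is correlated with a low G1 outcome. Results are at 11% / 28% / 44% drop-out:

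| Correlation | P2 (truth 0) | A4 (truth 0.3) |
|---|---|---|
| 0 | 0.01 / 0.00 / 0.00 | 0.29 / 0.30 / 0.30 |
| 0.3 | 0.50 / 0.36 / 0.26 | −0.20 / −0.06 / 0.04 |
| 0.6 | 1.01 / 0.72 / 0.53 | −0.71 / −0.42 / −0.23 |

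**The A4 test.** P1 yields one difference per returning patient. P2 is a difference between the means of two separate groups and yields none, so there is no second sample for an unpaired t-test. The contrast itself has an ordinary variance: var(paired change)/n(returners) + var(PDP6)/n6 + var(PDP7)/n7.

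**The alternative contrasts.** Comparing PDP7 with all first-time G1 users (PDP4 + PDP6) gives M7 − m = S. The paired change minus that gives (S + X) − S = X. In simulations of the SUS set-up the bias of this system contrast was about 0, against 6.7 to 8.8 points for P2.

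**The case against.** The strongest reply is that bias is not shown. No drop-out rate and no link between drop-out and outcome is documented. Death, investigator withdrawal and simple loss over 16 to 18 months need not track experience with G1. This stands: a reader might infer that P2 and A4 are biased, and in G2's favour, but the documents do not establish that, since D could be zero or of either sign.

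Second, a reader might infer that G2-only patients are purely replacements for drop-outs. Section 7.2 makes that recruitment conditional, and Sections 4.1 and 4.4.2 treat first-time G2 patients as a planned group. What is certain is that they are new recruits. That G1-only patients are mainly non-returners is an inference, though a strong one given the inclusion criterion and the retention aim.

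Third, the worked SUS example concerns M1, while Section 9.1 calls M2 and M3 the critical metrics. This also stands. User-dependent measures (M1, M2.1, M2.2, M2.4, M2.5) are most exposed. M2.3 and M3 are computed by the system and are affected mainly through record content. M4 is in neither P2 nor A4.

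Fourth, it would be too strong to say that A4 cannot be tested at all. Only the named test fails; the contrast can be tested with a combined standard error.

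Last, this is a proof-of-concept study, and a statistical analysis plan that is not shown could add adjustment. But the protocol itself fixes the contrast, the test and the causal reading, and nothing in Section 9 qualifies them.

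**Conclusion.** The point holds in this form. P2 is a non-randomised comparison of patients who in effect did not return with new recruits. It is open to selective drop-out and cannot be read as labelled. A4 carries the same selection difference with the opposite sign, so its reading as an experience effect is equally unsupported, and its unpaired t-test cannot be run as named.

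The structural conclusion needs no numerical assumption. The size does: 6.7 SUS points and 39% false significance rest on w = 2/3, d = 10, SD 15 and 30 per group, and across the assumed ranges the false-significance rate runs from 7% to 95%. If few G2-only patients are recruited, P2 and A4 will be barely estimable whatever the bias.

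**What to change.** 1. **System effect:** compare first-time G2 users (PDP7) with all first-time G1 users (PDP4 + PDP6), adjusted for site, therapeutic area and the health and digital literacy scores at each patient's first entry. Do not use the scores re-measured at G2 for returners, since that could adjust away part of the experience effect.
2. **Experience effect:** take the mean paired change in returners minus that system effect, with a standard error that allows for patients contributing to both parts (for example a bootstrap by patient). Give a random-patient-effect model as a second estimate, and state that the two rest on different drop-out assumptions. With a true effect of 5 SUS points in simulation, the model gave about 6.6 to 6.9 and the simple contrast 5.0 under the set-up above (within-patient correlation 0.5). When drop-out depended on the observed G1 score, they gave about 4.9 to 5.5 and 2.8 to 3.0.
3. **Check:** report PDP6 against PDP4 at G1 as direct evidence on selective drop-out.
4. **Wording:** replace "effect of system only" and "There is a difference in performance due to training/experience with the system" with text saying that the comparison is non-randomised and assumes that G2 recruits resemble the original G1 entrants.

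The cost is a little more analysis work and a more cautious causal claim. No new data are needed, because literacy is already recorded before each evaluation (Section 10.3.1). Two limits remain: the resemblance assumption is reduced by the covariates but not removed, and patients lost before the usability questionnaire at Week 2 Day 5 still have no M1 score.

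### P2 is labelled a pure system effect, but it compares G1 patients who did not return with newcomers at G2; if not returning is related to the G1 experience, P2 favours G2 and A4 understates or reverses the experience effect

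*Protocol*

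**What the plan says.** Section 9.3 defines P2 for usability as "M1@PDP6 - M1@PDP7", with parallel formulas for M2 and M3. The test is unpaired and its meaning is given as "effect of system only". A4 is P1 minus P2 and is read as the effect of training or experience.

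The groups behind P2 come from the Single Generation arm, defined in section 4.1 as "patients who contribute to the evaluation of only one generation of the prototype (G1 or G2"). No randomisation or advance assignment to that arm is described. Among the mandatory inclusion criteria in section 5.2 is "Agree to test the AIDAVA prototype (G1 and G2) and to delegate to a representative data curator in case of issues". The introduction to the deliverable says "it was decided to keep as much of the same patient as possible across the 2 generations of the prototype". On new patients at G2, section 7.2 says "In case of an important discontinuation we might need to ask sites to recruit new patients for EPOCH 3" (from the context, the G2 assessment, which section 4.1 numbers Epoch 4).

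Neither P2 nor A4 carries a caveat about why some patients were seen at G1 only.

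**The concern.** Membership of PDP6 is settled after a patient has used G1, and possibly because of that use. PDP7 has passed through no such filter. A contrast between the two mixes the change of prototype with whatever separates leavers from the rest of the G1 intake.

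This touches the primary hypothesis. Section 9.1 states under H1 that the improvement is due mainly to the tool, with some due to training. P1 is labelled as system plus experience, and A3 pools all patients, so only P2 and A4 address that split.

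The comparison also drops PDP4. Those patients were first-time users at G1 as well, and with moderate drop-out they are most of the G1 sample.

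**Working it through.** **Who is in each group**

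| Data point | Generation | Patients | Prior use |
|---|---|---|---|
| PDP4 | G1 | returners | none |
| PDP5 | G2 | returners | yes |
| PDP6 | G1 | did not return | none |
| PDP7 | G2 | newcomers | none |

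An experience-free comparison of G1 with G2 is PDP4 + PDP6 against PDP7. P2 uses PDP6 against PDP7.

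**Inputs from the protocol.** Planned total: 3 sites x 2 use cases x 15 = 90 patients, which reproduces section 9.4. That section expects some drop-out without giving a rate, and assumes 50 to 80 subjects are enough. That leaves room for 10 to 40 losses, or 10/90 = 11% to 40/90 = 44%. No SD, alpha, power or effect size is stated.

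**Assumptions not in the protocol.** Within-patient correlation r = 0.5; two-sided alpha 0.05, so 2.5% in the direction of G2; newcomers equal in number to leavers and drawn from the same population as the G1 intake; G1 and G2 identical; no experience effect.

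**Bias formula.** Let d be the drop-out fraction, rho the correlation between the G1 score and staying, z_d the normal quantile of d, and phi the normal density. On the protocol's scale (G1 minus G2, higher SUS better):

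- E[P2] = -rho x SD x phi(z_d)/d
- E[P1] = +rho x SD x (1 - r) x phi(z_d)/(1 - d)
- E[A4] = E[P1] - E[P2]

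Take 25 leavers, d = 25/90 = 0.278, z_d = -0.589, phi = 0.335, rho = 0.4 and an assumed SUS SD of 20:

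- P2 = -0.4 x 20 x 0.335/0.278 = -9.7 points, a false gain for G2
- P1 = 0.4 x 20 x 0.5 x 0.335/0.722 = +1.9 points, regression to the mean among returners
- A4 = 1.9 + 9.7 = +11.5 points (from unrounded terms)

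A beneficial experience effect would make P1 more negative than P2, hence A4 negative. A positive A4 therefore looks like harm from experience when the truth is zero. With 10 to 40 leavers and rho from 0.2 to 0.6, the P2 bias runs from -3.6 to -20.5 points and the A4 bias from +5.0 to +21.7. At rho = 0 both are zero.

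**Simulation by odds ratio** (4,000 studies per row, 25% drop-out; OR = odds of leaving per SD worse G1 score):

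| OR | False G2 gain in P2 | False finding for G2 |
|---|---|---|
| 1 | 0 SD | about 2.5% |
| 1.5 | about 0.3 SD | about 16% |
| 2 | about 0.5 SD | about 36% |
| 3 | about 0.7 SD | about 65% |

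At OR 2 the A4 error is 0.56 SD: 0.48 from P2 and about 0.08 from P1. At OR 2 with 15% and 40% drop-out, the false-finding rates are about 29% and 37%.

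**The alternative, PDP4 + PDP6 against PDP7.** Mean bias is about 0 and false findings stay near the nominal 2.5% under the same assumptions.

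**Precision when drop-out is unrelated.** At d = 0.25 each P2 group has 22.5 patients on average:

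- SE of P2 = sqrt(1/22.5 + 1/22.5) = 0.298 SD
- SE using all G1 patients = sqrt(1/90 + 1/22.5) = 0.236 SD
- ratio = 0.298/0.236 = 1.26, consistent with the 25-30% excess seen in simulation

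**The case against.** The protocol does not say why patients will leave. Section 7.2 ties the risk to the 16 to 18 month gap. CVD patients enter after an acute infarction, and the follow-up form records death. Illness, death and lost contact need not track the G1 score, and without such a link there is no bias. This stands: direction and size are conditional. It does not support the label. Section 7.2 also connects discontinuation to interest ("To decrease the risk and keep the momentum / interest of patients we will issue regular newsletters"), section 7.1 allows withdrawal for behavioural or compliance reasons, and P2 has no protection if leaving is selective.

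The single-generation group is listed as a design arm, and newcomers have their own G2 screening window, so they are not only ad hoc replacements. The criterion "Agree to test the AIDAVA prototype (G1 and G2") cannot bind newcomers literally, since they cannot test G1. Both points are fair and concern PDP7. They do not create a planned G1-only group.

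The mechanism is direct for M1. Section 9.1 names M2 and M3 as the critical metrics, and parts of these are computed by the system. For them the bias arises only if leavers were also slower or had poorer records.

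A reader might infer that the whole claim that G2 improves on G1 is compromised. It is not: P1 compares within patients and A3 compares all G1 with all G2 patients. A reader might also infer that A4 inflates the experience effect. P2 is subtracted, so the effect is understated or reversed.

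**Conclusion.** The point holds in conditional form and should be fixed before analysis. It follows from the protocol's own text that P2 contrasts non-returners with newcomers, so the label is not earned. That P2 favours G2 requires drop-out related to the G1 experience, which the documents neither state nor exclude. The reading that dislike of G1 will be counted as improvement in G2 goes further than they allow.

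The illustrated sizes rest on assumed drop-out, odds ratios, correlation and one-for-one replacement. The loss of precision does not depend on selective drop-out. What is at stake is the tool-versus-experience part of H1. In a self-described proof of concept whose overall G2-versus-G1 comparison stands elsewhere, this is a should-fix rather than a must-fix.

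**What to change.** In section 9.3:

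- Redefine P2 as first-time users of G1 (PDP4 + PDP6) against first-time users of G2 (PDP7).
- Replace A4 by the prior-use term of one mixed model on PDP4 to PDP7, with generation, prior use and a random patient effect. In a 300-run check at 25% drop-out and OR 2, the system and experience terms were off by -0.03 and 0.02 SD, with two-sided false-positive rates of 4.3% and 5.0%.
- Replace the system-only label with: first-use comparison of G1 and G2.
- State the limits. The comparison assumes newcomers resemble the original intake, does not remove calendar-time differences, and depends on leavers consenting to use of their endpoints (section 7.1). The near-zero bias above is a consequence of the first assumption, not proof that the new P2 is unbiased.

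The cost is a few lines of wording and one model. No measurement beyond those already planned is needed.

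### Contrast A3 applies an independent-samples test to two samples that share patients, so for M1 to M3 its standard error is too large and power is lost

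*Protocol*

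**What the plan says.** All of this is in protocol Section 9.3 unless stated otherwise.

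- **A1 and A2.** A1 is defined as "Sum across patient arms for G1 A1.M1 = M1@PDP4 + M1@PDP6", and likewise for M2 to M4. A2 does the same for G2 with PDP5 and PDP7. Both rows are labelled descriptive statistics.
- **A3.** This is A1 minus A2: "Difference in A1 and A2 (i.e. difference between G1 and G2 across all patients". M1 to M3 get an unpaired t-test. M4 gets a Wilcoxon signed-rank test, with the hypothesis "The NLP system developed in G2 yields a higher precision than the NLP system from G1" and a matching one for recall.
- **P1.** "Difference in data points 4 and 5 (i.e. difference between G1 and G2 for arm where patients used G1" and G2: paired t-test.
- **P2.** "Difference in data points 6 and 7 (i.e. difference between G1 and G2 for arm where patients used G1" or G2: unpaired t-test.
- **U1 (secondary endpoints).** Also described as G1 versus G2 across all patients, but assigned a paired t-test.
- **The tests.** One of the three listed is "Mann-Whitney U test (unpaired t-test", described as being for independent groups. The signed-rank test is described as being for matched samples.

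On overlap, the Introduction of the main deliverable says "it was decided to keep as much of the same patient as possible across the 2 generations of the prototype". Section 5.2 makes willingness to test both generations an inclusion criterion. Section 7.2 foresees new recruits for the later evaluation only if discontinuation is substantial. No section gives an expected overlap.

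**The concern.** A3 mixes two kinds of patient. PDP4 and PDP5 are the same people measured twice; PDP6 and PDP7 are different people. The full G1 and G2 samples are therefore neither independent nor matched, and A3 meets neither of the protocol's own descriptions of the tests it uses.

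Section 9.1 makes superiority of G2 over G1 part of the primary objective, and A3 is the only patient contrast that tests it on everyone. If repeated values of a patient are positively correlated, the unpaired test overstates the standard error and can miss a real improvement.

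Three wording problems sit beside this:

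- *Sum* in A1 and A2 does not lead to a G1–G2 mean difference.
- The signed-rank test for M4 has no pair for single-generation patients.
- Equating the Mann-Whitney test with the unpaired t-test leaves open which one A3 uses.

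**Working it through.** **The plan's own figure.** Section 9.4: 15 patients × 3 sites × 2 use cases = 90. This is a head count. The protocol gives no alpha, SD, effect size or power for A3, so nothing further can be reproduced.

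**Assumptions.** SD = 1; 90 patients at G1 and 90 at G2; m of them in both; within-patient correlation ρ; nominal two-sided 5%.

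**Formulas.**
- Unpaired SE = √(1/90 + 1/90) = 0.1491.
- Correct SE of the same mean difference = √(1/90 + 1/90 − 2mρ/90²).
- Actual type I error = 2·[1 − Φ(1.96 × unpaired SE / correct SE)].

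Example, m = 72 and ρ = 0.5: 0.02222 − 72/8100 = 0.01333, so the correct SE is 0.1155. The ratio is 0.1491/0.1155 = 1.291, and 1.96 × 1.291 = 2.53 gives 0.011.

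| m (overlap) | ρ | Correct SE | Unpaired / correct | Actual type I error |
|---|---|---|---|---|
| 45 (50%) | 0.3 | 0.1374 | 1.085 | 0.034 |
| 45 | 0.5 | 0.1291 | 1.155 | 0.024 |
| 45 | 0.7 | 0.1202 | 1.240 | 0.015 |
| 72 (80%) | 0.3 | 0.1300 | 1.147 | 0.025 |
| 72 | 0.5 | 0.1155 | 1.291 | 0.011 |
| 72 | 0.7 | 0.0989 | 1.508 | 0.003 |

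Simulation (8,000 runs) at m = 72, ρ = 0.5 gave 0.014 for both the t-test and the Mann-Whitney test, so the ambiguity over the test's name does not rescue A3. The unpaired test is right only if m = 0 or ρ = 0. At ρ = −0.3 the error reverses, with type I error of about 0.07 to 0.08.

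**Power, and what P1 retains.** Take 72 repeat, 18 G1-only and 18 G2-only patients. A model using all records (generation effect and patient intercept only) has SE = √(2/[72/(1 − ρ) + 18]). At ρ = 0.5 this is √(2/162) = 0.1111, and 80% power needs an effect of 2.80 × 0.1111 = 0.311.
- Unpaired A3: (0.311 − 1.96 × 0.1491)/0.1155 = 0.17, power 57%.
- P1 alone: SE = √(2 × 0.5/72) = 0.1179; 0.311/0.1179 − 1.96 = 0.68, power 75%.

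At ρ = 0.3 / 0.5 / 0.7, unpaired A3 has 70 / 57 / 32% and P1 alone has 73 / 75 / 77%.

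**The sum.** Read as the sum of two arm means, A1 − A2 estimates twice the mean difference when the arm effects are equal, and weights the arms equally whatever their size. With 72 and 18 per generation and ρ = 0.5, its variance is 2 × 0.5/72 + 2/18 = 0.125. The SE is 0.354, or 0.177 after halving, against 0.115 for the pooled mean difference.

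**M4.** In the same scenario, a patient-level signed-rank test can use only the 72 repeat patients. The 18 G1-only and 18 G2-only patients have no pair.

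**The case against.** - **P1 already pairs the repeat patients for M1 to M3.** This stands. A reader might infer that the repeated-measures design is wasted, but P1 keeps 73 to 77% power in the scenario above. The loss belongs to A3, not to the whole plan.
- **A3 is not named as the leading contrast.** This also stands. Section 9.3 lists E1, E2, P1, P2, A3 and A4 without a hierarchy; Section 9.1 ranks metrics, not contrasts.
- **The error is conservative.** True for positive correlation. A reader might infer that A3 would produce false claims for G2; the arithmetic shows the opposite in that case.
- **The plus sign is probably shorthand for pooling.** Likely. The rows are labelled descriptive, the synopsis defines the M2 time measure as an average, and summing usability scores or precision over patients has no meaning. A reader might infer that fewer returning patients would by itself look like time saved: 72 against 90 at equal means gives totals 20% lower. The documents do not support that as an expected result. It needs dropouts not to be replaced and, more decisively, the named tests run on individual values, not on two totals. The wording still needs correcting.
- **M4 may be sound.** Section 3.1 defines it as NLP systems scored against an annotated gold standard. If both systems score the same documents, the signed-rank test is valid. The fault lies in listing M4 by patient arm in Sections 9.2 and 9.3, so it is an unresolved unit of analysis, not a proven wrong test.
- **The overlap is unknown.** Correct. The documents give an intention, expected dropout and possible replacement, so the size can only be a range.
- **U1 may involve different units,** since its secondary analysis set is built on data users. The contradiction with P1, which concerns the same patients and metrics, is the firmer one.

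**Conclusion.** The point holds for A3 on M1 to M3: by the protocol's own descriptions, an independent-samples test is assigned to samples that share patients. On the stated assumptions (90 per generation, 50 to 80% overlap, correlation 0.3 to 0.7), the standard error is about 8.5 to 51% too large and the nominal 5% test runs at about 3.4% down to 0.3%. The fault exists at any overlap above zero if the correlation is not zero; only its size rests on the assumptions. It costs power in one contrast and leaves P1 intact. The sum, the M4 unit and the merged test names need clarifying, but none is shown to bias a result. This should be fixed; it does not invalidate the plan.

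**What to change.** 1. **A3, M1 to M3.** Use one linear mixed model on all patient-generation records, with fixed effects for generation and prior G1 use and a random patient intercept. The prior-use term keeps system and experience effects apart, as P1, P2 and A4 intend. Adjustment for site, therapeutic area and literacy is optional.
2. **Name the A3 estimate.** In this model the generation coefficient is the effect in patients new to the system; adding the prior-use coefficient gives the change in repeat patients. An all-patient figure is the generation coefficient plus the prior-use coefficient times the share of repeat patients at G2.
3. **A1 and A2.** Replace the sum by pooled patient-level values summarised by means.
4. **M4.** State that the signed-rank test applies to units scored by both NLP systems: the same gold-standard documents, or repeat patients only.
5. **Tests.** List the unpaired t-test and the Mann-Whitney U test separately, and say which is used where.

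**Cost.** Wording in Section 9.3 and a little programming; no new visits. With high overlap the generation coefficient alone is imprecise: with 18 new patients at G2 its SE is about √(1/18 + 1/90) = 0.26 SD, so it should be read beside the all-patient figure. Pairing for M4 is limited to notes still held. Section 4.4 has patient data deleted after the evaluation report, keeping the G1 scores, while the End-of-Study section keeps the curated record until the project ends. These passages need reconciling first.
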